## 2. Objectives

Aim 1: To establish whether a smartphone otoscope improves diagnostic accuracy of tympanic membrane (TM) pathology for trainees, compared to supervisor.

Aim 2: To determine whether smartphone otoscope improves diagnostic confidence of trainees, thereby reducing frequency of antibiotic prescriptions for AOM.

Aim 3: To determine whether there is a change in repeat exam rates by supervisors, comparing with/without Cellscope.

Aim 4: To determine whether trainees convert to traditional otoscope use during the weeks that Cellscope is available.

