## 3. Study Procedures

### a. Study design, including the sequence and timing of study procedures

This is a prospective, randomized, unblinded, controlled study in the Harriet Lane Clinic (HLC), the Johns Hopkins Children's Center pediatric primary care resident teaching practice and the Johns Hopkins Children's Center Pediatric Emergency Department (Peds ED). The HLC has clinics for acute care (e.g., sick visits) and continuity (e.g., well child and follow-up visits). We will purchase Cellsopes, iPhones, phone cases, and locking storage systems for each setting. There will be no direct collaboration between the study investigators and Cellscope related to this study. We will evaluate the above aims by block-randomizing in 2-week blocks: 1 week where the Cellscope will be available and 1 week where only traditional otoscopy will be available. Because residents rotate through the HLC and Peds ED in 2 and 4-week rotations, this will allow for the inclusion of the same trainees in each arm to act as their own control and ensure there is no use of the Cellscope during the traditional-only weeks. During Cellscope weeks, the traditional direct otoscopes will be available based on trainee/supervisor preference. During the traditional weeks, the Cellscope will not be available, thus the standard of care will not be changed during our study. iPhones will be secured with 6-digit numeric passcodes, in compliance with JHMI security standards. Recordings/images of external and middle ear structures will be obtained in a HIPAA compliant manner without collecting any PHI.

During Cellscope weeks, trainees and supervisors will be given access to the Cellscope and asked to use this tool for their otoscopic exams (research procedure). They will have full discretion of when an otoscopic examination is indicated, based on their existing practice and standard of care. We will then ask that the

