trainees and supervisors each fill out an index card survey to record the following outcomes: agreement between trainee and supervisor using the OMgrade scale (validated otitis media diagnostic tool), trainee confidence in exam, antibiotic prescription, need for conversion to traditional otoscopy, and whether a repeat exam was obtained. During the traditional weeks, the Cellsopes will be unavailable, locked in an enclosure, and traditional otoscopy (routine care) will be the only method available. The same index card survey will be completed by the trainees and supervisors. There will be no change to patient restraint, as described above.

b. Study duration and number of study visits required of research participants.

The study will last for between 9-12 months depending on the number of patients enrolled. Only one study visit is required per research participant. The same patient will be able to be included in the study multiple times if they present to the HLC or Peds ED on multiple occasions.

c. Blinding, including justification for blinding or not blinding the trial, if applicable.

This study will be unblinded. It is not possible to perform this study in a blinded manner given the obvious difference in the handheld hardware.

d. Justification of why participants will not receive routine care or will have current therapy stopped.

Standard of care is traditional direct otoscopy, as described above. We are using an equivalent method of otoscopy that allows the identical visualization of the external and middle ear structures. It will also be explicitly stated to providers that they can revert to traditional otoscopy if they feel that the Cellscope is not able to identify the needed structures.

e. Justification for inclusion of a placebo or non-treatment group.

N/A

f. Definition of treatment failure or participant removal criteria.

If any provider feels that the Cellscope is not able to appropriately identify the needed ear structures, that will be considered a failure of the Cellscope, and that provider will be able to immediately revert to a traditional otoscope. Furthermore, patients and guardians may opt for providers to use the traditional otoscope at any time. This will be tracked.

g. Description of what happens to participants receiving therapy when study ends or if a participant's participation in the study ends prematurely.

Resumption of traditional care, without any harm to the patient.

h. Informed Consent

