If patients are interested in participating the trainees or supervisors will obtain informed verbal consent from the parent or legal guardian of the patient prior to examining the child. Explaining the study, obtaining consent, answering questions, and assessing parent and patient understanding is expected to take under 5 minutes, which is typical for a similar conversation clinical setting. A copy of the IRB protocol will be provided upon request. A waiver of written consent is requested because the consent document is the only record linking the subject and the research. The research presents no more than minimal risk of harm to subjects and involves no procedures for which written consent is normally required outside of the research context.

i. Provider Training

Providers will be trained on setting up the Cellscope: attaching the case to the iPhone, attaching the Cellscope to the case, turning on the iPhone and unlocking it. They will also be trained on how to use the Cellscope application to record non-PHI containing images/videos. This training will be done by members of the study team who are proficient in using the device and app. This will occur in whatever clinical setting, in which they are assigned (Pediatric Emergency Room, Harriet Lane Acute Clinic, Harriet Lane Continuity Clinic). This will take place prior to them using the device on any patients for the purposes of this study or any other indication.

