**5. Study Statistics**

a. Primary outcome variable.

Aim 1:

- A. Inter-rater reliability between trainee and supervisor utilizing the OMgrade scale

Aim 2:

- A. Rates of patients who receive antibiotics

- B. Levels of provider confidence in exam based on a standardized confidence measure

Aim 3: Rate of repeat exams by supervisors with and without Cellscope

b. Secondary outcome variables.

Aim 4: Rate of provider decided use of traditional otoscopy during Cellscope weeks

c. Statistical plan including sample size justification and interim data analysis.

Descriptive statistics will be performed to analyze our outcome measures in conjunction with Johns Hopkins BEAD Core statisticians.

1. Calculation of descriptive statistics such as mean, median, SD, range will be employed.
2. Examination of graphs such as outcome vs. time, scatterplots of two variables, Kaplan-Meier curves.
3. Estimation of differences between two groups with comparison by t-test or Mann-Whitney test.
4. Estimation and testing of within-person changes by matched t-test or Wilcoxon signed-rank test.
5. Multiple linear regression, logistic regression, or Cox proportional hazards regression.
6. Repeated measures models (usually requires the help of a statistician).
7. Comparison of proportions by the determination of kappa values will be employed.
8. Sample size will be calculated with an alpha of 0.05 and power of 80% to detect a change of 10%.  
We will have a minimum sample size of 392 subjects based on this calculation.

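### Aim 2 concerns antibiotics for AOM, but primary outcome 2A and the described card item name no indication, so 2A as written does not directly answer Aim 2

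*Combined protocol and SAP*

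**What the plan says.** Section 2 (Objectives) links Aim 2 to a named indication: better trainee confidence is expected to act by "thereby reducing frequency of antibiotic prescriptions for AOM". Section 5a lists two primary outcomes under Aim 2. The first, 2A, is "Rates of patients who receive antibiotics"; the second is provider confidence.

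The data source is the index card described in section 3a. Its listed contents include "trainee confidence in exam, antibiotic prescription, need for conversion to traditional otoscopy" and "agreement between trainee and supervisor using the OMgrade scale". The card itself is not reproduced.

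Section 4 admits all ages and any patient for whom the clinical team would do otoscopy, with no exclusions. Section 3a names the settings: the pediatric emergency department, and a primary care practice that sees sick, well-child and follow-up visits. Section 3c states: "This study will be unblinded".

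**The concern.** The aim is specific to an indication and the outcome is not. The enrolled population is not restricted to suspected ear infection, so some patients can be expected to receive an antibiotic for something else. Counted literally, those prescriptions enter 2A.

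Two things follow. First, the estimate answers a different question from the one in Aim 2: a null result on 2A would not rule out a fall in AOM prescribing, and a positive one would not show where the fall occurred. Second, other antibiotics dilute the relative effect. They shrink the absolute difference only where indications overlap, that is, where a child spared an AOM antibiotic receives one anyway for another reason.

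Timing matters too. Section 3h asks to waive written consent because "the consent document is the only record linking the subject and the research". This suggests that the cards carry no patient identifier, in which case an indication not recorded at the visit could probably not be recovered from the chart.

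**Working it through.** **Step 1. The texts side by side.**

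- Aim 2 (section 2): antibiotics, AOM named.
- Outcome 2A (section 5a): antibiotics, no indication.
- Card item (section 3a): antibiotic prescription, no indication in the description.
- Population (section 4): all otoscopy patients, no exclusions.
- Analysis (section 5c): nothing restricts the numerator or denominator of 2A, defines AOM from OMgrade, or links OMgrade to the prescription.

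The mismatch is established by this comparison and needs no figure. The remaining steps only illustrate its possible size.

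**Step 2. The plan's own figure.** Section 5c item 8 gives alpha 0.05, power 80%, a change of 10% and a minimum of 392 subjects. It names no outcome, baseline rate or sidedness, and does not say whether 392 is a total or a number per arm. It can be reached in at least two ways, with 2.80 = 1.96 + 0.84:

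- 20% vs 10%, unpooled variance: (0.20×0.80 + 0.10×0.90) × 2.80² / 0.10² = 0.25 × 7.84 / 0.01 = 196 per arm, 392 in total. The pooled formula gives 199 per arm, 398 in total.
- Rates near 50%: 2 × 0.25 × 2.80² / 0.10² = 392 per arm. The pooled formula at 45% vs 55% also gives 392 per arm.

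Nothing ties either to 2A. I use 196 and 392 per arm only as plausible sizes.

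**Step 3. Dilution under assumed rates.** Let p be the AOM-antibiotic rate in an arm and o the rate of other antibiotics, taken as equal in both arms. All rates here are assumptions.

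- No overlap: any-antibiotic rate = p + o.
- Independent overlap: any-antibiotic rate = p + (1 − p) × o.

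Power is for a two-sided pooled test at 0.05: Φ[(d − 1.96 × se0) / se1], where d is the difference, se0 = √(2 × p̄(1 − p̄)/n), p̄ is the mean of the two rates, and se1 = √((p1(1 − p1) + p2(1 − p2))/n). Clustering by week, provider and repeat patient is ignored.

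One case in full: AOM 20% vs 10%, o = 10%, no overlap, 196 per arm. The rates become 30% vs 20%; se0 = √(2 × 0.25 × 0.75/196) = 0.0437; se1 = √((0.21 + 0.16)/196) = 0.0434; power = Φ[(0.10 − 0.0857)/0.0434] = Φ(0.33) = 63%.

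| AOM rates | Other (o) | Overlap | Any antibiotic | Relative reduction | Difference (points) | Power, 196/arm | Power, 392/arm |
|---|---|---|---|---|---|---|---|
| 20 vs 10 | 0% | n/a | 20 vs 10 | 50% | 10 | 79% | 98% |
| 20 vs 10 | 10% | none | 30 vs 20 | 33% | 10 | 63% | 90% |
| 20 vs 10 | 20% | none | 40 vs 30 | 25% | 10 | 55% | 84% |
| 20 vs 10 | 10% | independent | 28 vs 19 | 32% | 9 | 56% | 85% |
| 20 vs 10 | 20% | independent | 36 vs 28 | 22% | 8 | 40% | 67% |
| 50 vs 40 | 0% | n/a | 50 vs 40 | 20% | 10 | not shown | 80% |
| 50 vs 40 | 10% | none | 60 vs 50 | 17% | 10 | not shown | 80% |
| 50 vs 40 | 20% | none | 70 vs 60 | 14% | 10 | not shown | 84% |
| 50 vs 40 | 10% | independent | 55 vs 46 | 16% | 9 | not shown | 71% |
| 50 vs 40 | 20% | independent | 60 vs 52 | 13% | 8 | not shown | 62% |

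The relative reduction is diluted in every row with other antibiotics. Power is not: in the no-overlap rows at 50% vs 40% it is unchanged or slightly higher.

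**The case against.** The best defence is that 2A is shorthand. It sits under the Aim 2 label in a terse list, and Aim 2 already names AOM. That is a natural reading, and it would align outcome and aim. But no text says so, and the card would then have to record the indication.

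The card is not shown, so an indication field may exist. This stands: a reader might infer that the indication will not be collected, but section 3a is a running list of topics, not the item wording.

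The card also carries OMgrade, so prescribing could be tabulated among ears graded as otitis media. This is partly right. OMgrade is a proxy for the reason for prescribing, and the plan does not describe this use of it.

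The any-antibiotic rate is itself a defensible outcome. Weeks are randomised, so antibiotics that the device does not affect should balance in expectation. The rate does not depend on a label chosen by an unblinded prescriber. It also captures other ear antibiotics that the device might influence, since the external ear is imaged too ("Recordings/images of external and middle ear structures will be obtained"). This stands, and it is a reason not to discard or automatically demote that rate.

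Lastly, irrecoverability is inferred from a consent-waiver justification, not from a description of data linkage. It is a reason for care, not a finding.

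**Conclusion.** The point holds as a mismatch between an aim and its primary outcome. Followed as written, 2A counts antibiotics for any indication, so it does not directly answer Aim 2. It is not uninformative, because the overall rate partly reflects AOM prescribing.

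A reader might go further and infer that the trial is underpowered for Aim 2. The documents do not support that. They give no prescribing rates, and the 392 is not tied to 2A. The illustration runs from a fall of 79% to 40% (20% vs 10%, other antibiotics at 20% with independent overlap, 196 per arm) to no loss at all (50% vs 40%, no overlap, 392 per arm). The size of any power loss is unknown.

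Confidence is moderate because the card is unseen. If it already records the indication, only the wording of 2A needs to change. The matter deserves correction because 2A is a listed primary outcome and the remedy is cheap before data collection but may be unavailable after it.

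**What to change.** 1. Check the card. Unless it already captures the indication, add one item: *Antibiotic: none / for AOM (alone or with another indication) / other indication only*.
2. State in section 5a that Aim 2 is answered by the proportion of all enrolled exams with an antibiotic prescribed for AOM. Exams are the natural unit because section 3b lets a patient enter more than once.
3. Always report the any-antibiotic rate beside it. The sponsor may keep both under 2A rather than demote either, and should say in advance how they will be read together.
4. Cross-check the AOM label against the supervisor's OMgrade, by arm.

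The cost is one tick-box and a rewording of 2A. The downside is that unblinded prescribers assign the indication, so relabelling is possible and could favour the device. A fall in AOM-labelled antibiotics without a matching fall in the any-antibiotic rate should therefore be read with caution. Steps 3 and 4 limit this risk but do not remove it.

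### Aim 3 counts a supervisor's decision, but own controls are secured only for trainees, and no listed card item or analysis method identifies the supervisor

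*Combined protocol and SAP*

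**What the plan says.** Section 5a lists as a primary outcome for Aim 3 the "Rate of repeat exams by supervisors with and without Cellscope". Section 2 words the aim in the same way, so the person who acts is the supervisor.

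Section 3a describes the randomisation: "We will evaluate the above aims by block-randomizing in 2-week blocks: 1 week where the Cellscope will be available", and the other week has traditional otoscopy only. The block length is justified by the length of resident rotations, and "this will allow for the inclusion of the same trainees in each arm to act as their own control". No supervisor schedule is given, and nothing places the same supervisors in both weeks of a block. Section 1 defines supervisors broadly: attendings, emergency medicine fellows, preceptors and nurse practitioners.

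The card content listed in section 3a covers agreement on the otitis scale, trainee confidence, antibiotics, conversion to traditional otoscopy and repeat examination. No supervisor identifier is among these items.

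Section 5c lists general methods: two-group tests, regression, repeated measures models, and "Estimation and testing of within-person changes by matched t-test or Wilcoxon signed-rank test". It assigns none of them to Aim 3, and does not say which person is meant in the matched test. The sample size rests on "power of 80% to detect a change of 10" per cent and ends with "We will have a minimum sample size of 392 subjects based on this calculation". No allowance for clustering is mentioned.

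**The concern.** Supervisors plausibly differ in how readily they repeat an examination, and one supervisor's habit applies to every trainee working under that person. Matching on the trainee does not remove this, because the same trainee may work under one supervisor in the Cellscope week and another in the traditional week.

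Two things are at stake. If a few supervisors each cover a whole week, a chance difference in their habits between arms enters the device contrast, and a test that treats visits as independent understates the uncertainty. If the same supervisors work in both arms, the naive test overstates it and gives up an available within-supervisor comparison. The analysis cannot be repaired later if the cards do not show who supervised.

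**Working it through.** **1. The plan's own figure.** No baseline rate is stated, and 392 is not said to be a total or per arm. With z-values 1.96 and 0.84, (1.96 + 0.84)² = 7.84, and 392 arises in two ways:
- per arm, with a difference of 0.10 and SD 0.5: 2 × 0.25 × 7.84 / 0.01 = 392;
- in total, for 10% against 20% with unpooled variance: 2 × (0.09 + 0.16) × 7.84 / 0.01 = 392.

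Both treat every visit as independent.

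**2. Inputs for the illustration.**
- From the documents: 392 visits (section 5c); 9 to 12 months, that is 39 to 52 weeks (section 3b); three settings (section 3i).
- Assumed, not in the documents: 392 is the total; visits are spread evenly; one supervisor covers each setting in each week; the correlation between visits under the same supervisor (ICC) is 0.05 to 0.20.

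**3. Case A: one supervisor per setting and week.**
- Visits per supervisor-week: m = 392 / (52 × 3) = 2.51 to 392 / (39 × 3) = 3.35.
- Design effect DE = 1 + (m − 1) × ICC. Low end: 1 + 1.51 × 0.05 = 1.08. High end: 1 + 2.35 × 0.20 = 1.47.
- Power = Φ(2.80/√DE − 1.96). Low end: Φ(0.74) = 77%. High end: Φ(0.35) = 64%.
- If 392 is per arm, the total is 784 and m = 5.03 to 6.70. DE is then 1 + 4.03 × 0.05 = 1.20 to 1 + 5.70 × 0.20 = 2.14, and power is about 72% to 48%.

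**4. Case B: each supervisor divides evenly over both arms.** The naive interval is too wide by the factor 1/√(1 − ICC): 1/√0.95 = 1.03 to 1/√0.80 = 1.12.

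**5. Simulation of the rota.** No device effect; 20 two-week blocks, 20 supervisors, 10 visits per week (400 visits), base rate 30%, 2,500 replicates. All these settings are assumed. Type I error of a naive test at nominal 5%:

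| Rota | ICC 0.02 | 0.05 | 0.10 | 0.20 |
|---|---|---|---|---|
| One supervisor per week, drawn anew | 6.8% | 10.2% | 15.9% | 23.4% |
| Two supervisors per week | 5.5% | 7.1% | 10.7% | 14.9% |
| Supervisors mixed visit by visit | 5.6% | 5.4% | 5.1% | 5.7% |
| Same supervisor in both weeks of a block | 5.3% | 4.8% | 4.3% | 3.4% |

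The first two rows use larger clusters than case A (10 visits per week in a single setting, against about 2.5 to 3.4 per setting), so they show direction and not the likely size here. A Mantel-Haenszel test stratified by supervisor stayed at 4.4% to 5.6% under every rota and ICC. The simulation contains supervisor effects only and no separate week effects.

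**The case against.** Much of the other side stands.

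- **Matched person.** A reader might infer that the matched analysis follows trainees only. Section 5c does not say so: the person is unspecified, and regression and repeated measures models are also listed. The fault is that nothing is specified for Aim 3.
- **Card items.** Section 3a lists the outcomes to be recorded, not identifiers. No trainee code, date or arm is listed either, although the design needs them. The absence of a supervisor code therefore shows that none is promised, not that none will be collected.
- **Antibiotics.** A reader might infer that prescribing (Aim 2A) turns on the supervisor in the same way. The documents name no prescriber, and section 2 ties antibiotics to trainee confidence. Supervisor influence is plausible but not stated.
- **Size.** One could take 20 to 40 supervisors with all their visits in one arm (m = 392/40 to 392/20, about 10 to 20). This gives design effects of 1.4 to 4.7 and power of 65% down to 25%. The arithmetic is right, but it requires every supervisor to stay in one arm for 9 to 12 months while both arms occur in every two-week block. Nothing in the documents suggests that.
- **Week-level analysis.** The week is the randomised unit. An analysis that respects week and block would carry supervisor variation between weeks into its error term, so its intervals would be valid without a supervisor term, which would then mainly buy precision. This is correct, but section 5c does not commit to such an analysis.

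**Conclusion.** For Aim 3 the point holds on the text: the outcome is the supervisor's act, own controls are secured only for trainees, and no listed card item or method identifies the supervisor. Because weeks are randomised, the consequence is unmodelled chance variation, unless supervisor rotas happen to follow the arm schedule, of which there is no sign.

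A reader might go further and say that the intervals are wrong. The documents do not support that. The direction and size depend on the rota and the ICC, and neither is given; with supervisors mixed visit by visit there is essentially no error. Under the assumptions of case A, the loss is moderate, and under case B it is a small inefficiency. For Aim 2A the point is only a reasonable precaution. Overall this is a cheap improvement that should be made before cards are used, not a fatal flaw.

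**What to change.** 1. Put an anonymous supervisor code on the index card.
2. Name the Aim 3 analysis: logistic regression of repeat examination on arm, with a supervisor effect in addition to the randomised week and block structure, so that the device effect is estimated within supervisor wherever a supervisor worked in both arms.
3. Apply the same model to Aim 2A as a supporting analysis.

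The cost is one card field and one model term. The downside is that supervisors must be told that coded data on their practice are kept.

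### Weeks are randomised within 2-week blocks, but section 5c commits no between-arm comparison to week or block, so the 5% error rate is not protected; the direction of the error is unknown

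*Combined protocol and SAP*

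**What the plan says.** Section 3a sets the unit of randomisation: "We will evaluate the above aims by block-randomizing in 2-week blocks: 1 week where the Cellscope will be available", with the other week of the block limited to traditional otoscopy. It justifies the scheme by trainee rotations: "this will allow for the inclusion of the same trainees in each arm to act as their own control".

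Section 5c lists methods in general terms. Item 3 is "Estimation of differences between two groups with comparison by t-test or Mann-Whitney test". Item 4 is "Estimation and testing of within-person changes by matched t-test or Wilcoxon signed-rank test". Item 5 offers linear, logistic or Cox regression, item 6 repeated measures models, and item 7 kappa. None mentions week, block or setting. Item 8 gives alpha 0.05, 80% power, a 10% change and a minimum of 392 subjects. It gives no baseline rate, intracluster correlation (ICC) or number of weeks, and does not say whether 392 is a total or per arm.

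Three other statements matter. On duration, section 3b says "The study will last for between 9-12 months depending on the number of patients enrolled". It also says "The same patient will be able to be included in the study multiple times". On sites, section 3a says "We will purchase Cellsopes, iPhones, phone cases, and locking storage systems for each setting", and section 3i on training says "This will occur in whatever clinical setting, in which they are assigned", naming the emergency department, the acute clinic and the continuity clinic. Nothing says whether these settings change arm in the same weeks.

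**The concern.** All exams in a given week (within a setting, if settings are randomised separately) are assigned together. They may share that week's supervisors and case mix. An unpaired test on individual exams treats them as independent, so its standard error can be wrong in either direction:

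- Correlation specific to a week makes the test reject too often.
- Correlation shared by both weeks of a block, such as season or the same trainees, cancels in a within-block comparison. If weeks are of similar size, an unpaired test that ignores it is nominal or conservative.

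The comparisons at stake are the primary outcomes: trainee-supervisor agreement, antibiotic rate, confidence and repeat-exam rate. The plan allows both an exam-level test and a block-aware model for them, and the two need not agree. Leaving the choice open until the data are in is undesirable in an unblinded trial.

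**Working it through.** **Inputs.** From section 5c: alpha 0.05 (taken as two-sided), power 80%, change of 10% (taken as 10 percentage points), 392 subjects. From section 3b: 9 to 12 months, so about 39 to 52 weeks, or 19 to 26 complete blocks. Every ICC and baseline rate below is an assumption.

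**1. Where 392 comes from.** With z-values 1.96 and 0.84, (1.96 + 0.84)² = 7.84. Three readings give 392, and none allows for week clustering:

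- Per arm near 50%: 7.84 × 0.50 / 0.10² = 392, total 784. The pooled formula at 45% v 55% also gives 392 per arm.
- Total for 10% v 20%: 7.84 × (0.09 + 0.16) / 0.10² = 196 per arm, total 392. The pooled formula gives 199 per arm, total 398.
- Pairs at 50% discordance: 7.84 × 0.50 / 0.10² = 392.

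The plan does not say which was used.

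**2. Unpaired exam-level test, week-specific correlation only.** With equal weeks, m = N / (weeks × settings), DEFF = 1 + (m − 1) × ICC, and true error = 2 × [1 − Φ(1.96 / √DEFF)]. Example: 392 exams over 39 weeks, one cluster per week, gives m = 10.05. At ICC 0.05, DEFF = 1.453 and the error is 10.4%. Ranges over 52 to 39 weeks:

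| Basis | ICC 0.02 | ICC 0.05 | ICC 0.10 |
|---|---|---|---|
| 392 total, one cluster per week | 6.5-7.1% | 8.9-10.4% | 12.7-15.6% |
| 392 total, two independent settings | 5.6-5.9% | 6.6-7.4% | 8.3-9.8% |
| 392 total, three independent settings | 5.3-5.5% | 5.9-6.4% | 6.8-7.8% |
| 392 per arm, one cluster per week | 8.3-9.5% | 13.3-16.1% | 20.7-25.1% |

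**3. Unpaired test, block-shared correlation only.** With equal weeks the variance of the arm difference is multiplied by 1 − ICC, so the error is 2 × [1 − Φ(1.96 / √(1 − ICC))]: 4.4% at ICC 0.05 and 2.8% at 0.20. Simulation with a continuous outcome and 392 total gave 4.4-4.7% and 2.9-3.0%. Simulation with a binary outcome at block ICC 0.05 gave 4.7-5.3% with similar-size weeks, but 6.9-7.6% when weekly numbers were very unequal.

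**4. A test that follows the randomisation.** In the continuous-outcome simulations (20 or 26 blocks, equal weeks), a paired t-test on block differences rejected 4.7-5.2% of the time in every mix of week and block correlation. In the binary simulations, including unequal weeks, a within-block permutation test stayed at 4.2-5.9%.

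**5. Power of the block-paired t-test, 392 total, equal weeks, one cluster per week.** Without clustering the noncentrality is 0.10 / √[(p₁q₁ + p₂q₂) / 196], where q = 1 − p: 2.80 for 10% v 20%, 1.99 for 45% v 55%, 3.35 for 5% v 15%. Degrees of freedom are 18 (39 weeks) or 25 (52 weeks).

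| Assumption | Power |
|---|---|
| 10% v 20%, no clustering | 75-77% |
| 45% v 55%, no clustering | 47-48% |
| 5% v 15%, no clustering | 89-90% |
| 10% v 20%, week-specific ICC 0.02 | 68-72% |
| 10% v 20%, week-specific ICC 0.05 | 59-65% |
| 10% v 20%, block-shared ICC 0.10 | 80-81% |

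Week-specific correlation divides the noncentrality by √DEFF; block-shared correlation divides it by √(1 − ICC). The assumed baseline moves power more than any of these ICCs does.

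**The case against.** The strongest reply is that section 5c is a menu and does not choose the unpaired test. Item 4 fits the own-control rationale of section 3a if the person is the trainee, which is the natural reading. Items 5 and 6 could be specified with block and week terms. Kappa in item 7 evidently serves the agreement outcome of Aim 1. The section also says that institutional statisticians will be involved. All of this stands: the plan does not rule out a suitable analysis, and it is not accurate to say that its methods have no connection to the outcomes. What remains is that no comparison is committed to the randomised unit. Pairing on trainee does not fully follow a randomisation of weeks.

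The second reply is that the size is assumed. This also stands. With three independent settings and ICC 0.02, the error is 5.3-5.5%, which is negligible.

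A reader might infer that the false-positive rate is inflated, or that a sound analysis would leave the trial below 80% power. The documents support neither. They give no ICC, block-shared correlation works in the other direction, and power for 392 total ranges from 47% to 90% with the assumed baseline alone.

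Finally, an analysis by week and block handles correlation but not selective enrolment. Clinic staff take consent in a week whose arm is known, and no choice of test removes that.

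**Conclusion.** The concern holds as a failure to commit, and it should be fixed. Weeks within 2-week blocks are randomised, no between-arm comparison is tied to them, and 392 matches only calculations without week clustering. An exam-level unpaired test, which the plan permits, would not protect the 5% level. Under assumed week-specific ICCs of 0.02 to 0.10 with equal weeks and 392 in total, its error would be about 6.5-15.6% with one cluster per calendar week, or 5.3-7.8% with three independent settings. Under block-shared correlation alone with similar-size weeks it would be nominal or conservative. The need to follow the randomisation does not depend on any particular ICC, because a block-based test holds about 5% in both situations. That this calls for one specific test, or for a larger trial, would be a further inference that the documents do not support.

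**What to change.** For antibiotic rate, confidence, repeat-exam rate and the between-arm difference in kappa, name one primary analysis in section 5c. It should keep each exam in the arm of its randomised week and compare arms within 2-week blocks, within setting if settings are randomised separately. Any of these is acceptable:

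- a block-paired test;
- a within-block permutation test;
- a regression with block as stratum and a random week effect, using small-sample degrees of freedom.

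State whether the settings change arm together. Make sure that week and setting are recorded with each exam; section 3a does not list them among the index-card outcomes, although the card itself is not shown. State whether 392 is a total or per arm, and the baseline rate behind it. Restate power over a range of assumed week and block ICCs, with the assumption attached to every figure.

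The cost is wording, a little more analysis work, and a stated power that may be less favourable. Enrolment need not change.
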